6 STATISTICAL METHODS

6.1 General Considerations

The statistical analyses will be performed using SAS Version 9.4 (or higher). All tables, figures and listings will be produced in landscape format.

Data will be presented at each scheduled timepoint (nominal time), where applicable. However, time-related endpoints (time to event) will be summarized using actual time.

For actual time, two reference points will be used: (a) decision to dose and/or (b) injection of study drug, which are specified in the primary and secondary endpoint analyses.

The total number of subjects in the study group (N) under the stated population will be displayed in the header of summary tables.

All study data will be included in the study data listings. Listings will be displayed by subject in chronological order, if not stated otherwise.

For tabulated safety summaries, only the scheduled timepoints will be included in the summary tables. Unscheduled assessments will be listed and used for evaluation of worst post-baseline value in categorical assessments, where applicable.

Sample codes and calculations for the efficacy analysis are provided in Appendix 2: Code Fragments. Actual code or procedure usage can differ from these samples, based on the model and conditions that correspond to those pre-specified in the SAP. Additional analysis may be performed for the cases not specified in SAP and will be described in CSR.

6.1.1 General guideline for descriptive summaries

For continuous variables, mean, median, standard deviation, minimum and maximum will be presented for each treatment group and category.

Additionally, coefficient of variation, geometric mean and geometric coefficient of variation will be calculated for: C_{max} , AUC_{0-90} and AUC_{0-180} .

For categorical variables, count and percent of subjects/counts in each treatment group and category will be presented. Percentages will be based on number of subjects with non-missing values, if not specified otherwise.

6.2 Euglycemic Baseline

Prior to starting the hypoglycemia induction procedure, the subject must have stable plasma glucose for at least 30 minutes at 95 ± 20 mg/dL (75 to 115 mg/dL [4.17 to 6.38 mmol/L]) at a stable IV insulin infusion rate varying no more than $\pm 20\%$ during which plasma glucose must be measured at least every 15 ± 2 minutes (i.e., at least 3 consecutive values in the target range at 0, 15, and 30 minutes).

For Hypoglycemia Symptoms Assessment scheduled at the end of the Euglycemic Baseline phase just before the IV bolus push dose of insulin, will serve as baseline to determine hypoglycemia symptoms relief and/or resolution. If more than one assessment performed in this time interval, then the last assessment of each hypoglycemia symptom or score will be selected for baseline.

6.3 Hypoglycemic Baseline

Hypoglycemic steady state is defined as a confirmatory plasma glucose value ≥ 42 mg/dL (≥ 2.33 mmol/L) and < 54 mg/dL (< 3 mmol/L), and an 8-minute linearly extrapolated future plasma glucose value ≥ 42 mg/dL (≥ 2.33 mmol/L).

To determine whether a hypoglycemic steady state has been achieved, confirmatory plasma glucose measurements will be taken as necessary at 5, 10 and 15 minutes after an initial plasma glucose < 54 mg/dL (< 3 mmol/L). Depending on the outcome, the following procedures will be followed.

1. If any of the confirmatory measurements meets the criteria for hypoglycemic steady state, the subject will be eligible to receive study glucagon, and further confirmatory plasma glucose measurement are not required.
2. If the final confirmatory plasma glucose value is < 42 mg/dL (< 2.33 mmol/L), the procedure will be terminated, study glucagon will NOT be administered, and the visit will be rescheduled after a minimum 3-day wait. At the Investigator's discretion, the subject should be treated with IV glucose or oral carbohydrates, it should be verified that the subject achieved a euglycemic state and is medically stable prior to discharge.
3. If any of the confirmatory plasma glucose measurements are > 54 mg/dL (> 3 mmol/L), then the IV insulin infusion will be re-started, and insulin adjustments will be made as per the induction procedure. Once another initial plasma < 54 mg/dL (< 3 mmol/L) is obtained, the sequence of up to 3 confirmatory plasma glucose readings will repeated.

If the subject achieved hypoglycemic steady state their linearly extrapolated plasma glucose value from the last two readings of hypoglycemia induction to time of study drug administration will be defined as Hypoglycemic Baseline for corresponding treatment period and will serve as baseline for the Primary Endpoint and Secondary Endpoints related to pharmacokinetic and pharmacodynamic characteristics within Treatment Period 1 / 2.

6.4 General guideline for define the protocol time

Protocol time is needed to find the 30-minute glucose value as well as to generate most of the glucose or hypoglycemia score curves.

Protocol time will be developed based on the following procedures:

- Protocol time zero will be based on either receiving glucagon or decision to dose:
 - Receiving glucagon: T0 = actual time stamp of glucagon injection
 - Decision to dose: T0 = actual time stamp when dose decision is made

- Subsequent protocol times are calculated by the following minutes plus T0 (receiving glucagon):
 - 5, 10,15,20,25,30,35,40,45,50,55,60,65,70,75,80,85,90;
 - 120,150, and180.
- For any continuous (number) variable, the value at the protocol time will be determined by linear interpolation between the two adjacent time points.
- For any categorical (text) variable, the value at the protocol time will be determined using the nearest value:
 - Protocol time 5 – 85: -2 minute to +3 minute;
 - Protocol time 90: -2 minute to 15 minute;
 - Protocol time 120, 150, 180: -15 minute to +15 minute;
 - If multiple values are attributed to a single protocol time, then the last value will be used.

Several analyses will be conducted using both the protocol time based on study drug administration and the one based on decision to dose. These analyses will be noted in each of the corresponding sections.

6.5 Analysis of Primary Endpoint

The primary endpoint analysis will be based on the risk difference in rates of failing to achieve Positive Plasma Glucose Response (PGR) of G-Pen versus GlucaGen Hypokit and a 95% CI will be calculated. Non-inferiority will be declared if the upper limit of the 95% confidence interval for the difference in failure rates is $\leq 5\%$; where the absolute failure rate of G-Pen treatment is $\leq 5\%$. This analysis will be repeated for ITT, mITT and PP populations.

Subjects who are missing the primary endpoint for a study treatment will be considered as having a failure in the primary analysis for that treatment administration. This imputation will be conducted for both the ITT and the mITT populations. If a subject received the same two treatment administrations for both periods (Period 1 and Period 2), only the visit with the planned treatment received will be included in the primary analysis and the subject will be considered a failure in the primary analysis for the for unreceived treatment administration (ITT, mITT). For all other analyses, data will be included for only the planned treatment received in those analyses.

A sensitivity analysis will be performed for where all missing data will be considered a success and the same analysis as above completed.

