5.1.1 Intent-to-Treat Population (ITT)

The Intent-to-Treat (ITT) population is defined as all subjects randomized. A subject’s randomized treatment will be used for analysis regardless of the actual treatment received. ITT population will be used for all summaries except safety/tolerability and disposition (where Enrolled population will be used). Primary endpoint comparison and secondary efficacy analysis will be performed for ITT, mITT and PP populations.

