5.1.2 Modified Intent-to-Treat Population (mITT)

The Modified Intent-to-Treat (mITT) population is defined as all ITT subjects and received at least one dose of study drug. The actual treatment received will be used for analysis.

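### SAP 6.5 counts periods with no injection as drug failures in ITT and mITT, so leavers alone can decide non-inferiority, and nothing says which of ITT, mITT and PP decides

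*SAP*

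**What the plan says.** SAP 6.5 compares failure rates by a risk difference. Non-inferiority requires the upper 95% limit to be at most 5%, with a second condition: "where the absolute failure rate of G-Pen treatment is" also at most 5%.

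On missing data it says "Subjects who are missing the primary endpoint for a study treatment will be considered as having a failure in the primary analysis" for that administration, and "This imputation will be conducted for both the ITT and the mITT populations". SAP 5.1.1 says "The Intent-to-Treat (ITT) population is defined as all subjects randomized". SAP 5.1.2 says the mITT "population is defined as all ITT subjects and received at least one dose of study drug". Someone dosed in period 1 who never returns is therefore in both sets and is scored as a failure of the drug not given. The sentence starting "If a subject received the same two treatment administrations for both periods" deals only with subjects given one drug twice, and it scores the drug not received in the same way.

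On the choice of analysis: "This analysis will be repeated for ITT, mITT and PP populations". Then: "A sensitivity analysis will be performed for where all missing data will be considered a success". Protocol 13.3 lists ITT and PP. Neither document ranks the populations.

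Undosed periods can occur. Under Protocol 10.2.1.2, randomisation precedes confirmation of hypoglycaemic steady state, and a failed induction ends the visit without study drug. Visits may be rescheduled, and Protocol 7.2 allows up to four inductions.

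**The concern.** A subject who leaves between visits says nothing about whether the second drug would have raised glucose. When true failures are expected to be rare, such periods can outnumber real failures. The ITT result can then turn on which sequence lost one more subject. In the same data PP and missing = success can pass, so the trial's conclusion can depend on a choice among populations that the SAP does not make.

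**Working it through.** **The plan's own figure.** 111 × 1.10 = 122.1, i.e. 122 randomised (111 / 0.90 would give 124). This leaves 122 − 111 = 11 subjects (9.0%) not evaluable in both periods. The 111 cannot be rebuilt because no odds-ratio margin is stated. Its 80% power belongs to an odds-ratio test and is not used as a comparator here.

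**Inputs from the documents.** N = 122, taken as 61 per sequence (Protocol 9.1 asks for about equal numbers). Margin 5% and G-Pen cap 5% (SAP 6.5), so at most 6 G-Pen failures (0.05 × 122 = 6.1). Unpaired Wald limit from the `riskdiff` sample code (SAP Appendix 2).

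**Assumptions.** Each subject leaves between periods with probability d, unrelated to sequence. In steps 1 and 2 neither drug ever truly fails.

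**Step 1: single splits.** U = pG − pH + 1.96 √[pG(1 − pG)/122 + pH(1 − pH)/122]. For 6 G-Pen and 5 GlucaGen periods missed: 0.0492 − 0.0410 + 1.96 × 0.0266 = 0.0603.

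| Missed G-Pen / GlucaGen | Upper limit | Result |
|---|---|---|
| 2 / 0 | 3.89% | pass |
| 3 / 0 | 5.21% | fail |
| 5 / 6 | 4.39% | pass |
| 6 / 5 | 6.03% | fail |

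**Step 2: chance of passing ITT.** P = Σ Bin(a; 61, d) × Bin(b; 61, d) over all (a, b) with U ≤ 5% and a ≤ 6, where a and b are the missed G-Pen and GlucaGen periods.

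| d | 2% | 3% | 5% | 10% | exactly 11 leavers | exactly 12 leavers |
|---|---|---|---|---|---|---|
| P(pass) | 94% | 87% | 71% | 43% | 50% | 38% |

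PP and missing = success see 0 against 0 failures and always pass. Other choices lower the ITT figures. A Newcombe interval gives 74% at 2%, 54% at 5% and 36% at 10%. If half the leavers miss both periods, the unpaired interval gives 93%, 59% and 14%.

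**Step 3: false claims.** True failure 5% on G-Pen and 0% on GlucaGen, balanced leavers, SAP rule. The G-Pen count is Bin(61, 0.05) + Bin(61, d + 0.05(1 − d)); the GlucaGen count is Bin(61, d).

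| d | 0 | 0.5% | 1% | 2% | 3% | 5% | 10% |
|---|---|---|---|---|---|---|---|
| P(false claim) | 5.3% | 6.1% | 6.2% | 5.5% | 4.8% | 4.2% | 2.2% |

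The excess over 2.5% is already there with nobody missing, so it comes from the interval. Injected periods with the same unpaired Wald limit give 5.3 to 6.7%. With a hybrid-score limit they give 1.4 to 1.9%.

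**Step 4: what the full change costs.** Chance of passing when both drugs truly fail at the same low rate:

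| Undosed | 0 | 2% | 3% | 5% | 10% | Full change |
|---|---|---|---|---|---|---|
| SAP rule, 1% true failure | 94% | 79% | 71% | 59% | 32% | about 75% |
| SAP rule, 2% true failure | 79% | 65% | 59% | 49% | 22% | 57–59% |

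Restricting to injected periods costs almost nothing by itself: with unpaired Wald at 1% true failure it passes 92–94% at 0–10% undosed. The score interval is what costs power.

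**Step 5: why PP is not a safe default.** Suppose 5 G-Pen failures, 3 of them in period 1 in subjects who do not return, and no GlucaGen failure. PP has 2/119 against 0/119, upper limit 4.0%, and passes. ITT has 5/122 against 3/122, upper limit 6.1%, and fails. Injected periods have 5/122 against 0/119, hybrid-score limit 9.2%, and fail.

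**The case against.** Missing = failure in all randomised subjects is a recognised, pre-specified choice, bracketed here by missing = success and PP. The SAP does label missing = failure as primary over missing = success. Staff know the assignment, so leaving out undosed periods assumes that unblinded decisions not to dose carry no information. Rescheduling should keep undosed periods few, and where they are few the SAP rule passes more often than the full change. The score interval is also sensitive to a few events: 2 against 0 failures in 122 gives 5.8% and fails. The Appendix 2 code is only a sample (SAP 6.1).

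Most of this stands and limits the point. It does not settle which population decides, and it does not make an uninjected period evidence about the drug. The events that decide under the change would at least be real failures, or injected periods with no 30-minute result.

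A reader might infer from SAP 5.1.5, which uses treatment actually received, that mITT is left open. It is not: 6.5 imputes in mITT explicitly. Nor does the population label on the Appendix 1 non-inferiority tables prove a further conflict, since SAP section 8 says table names may change.

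**Conclusion.** The concern holds in a bounded form and should be fixed. Leavers alone can fail an effective drug in ITT, and also in mITT when they leave between periods. The chance that two fully effective drugs pass falls from 94% at 2% undosed to 43% at 10%, given 61 per sequence, the sample Wald code and leavers only between periods.

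Four stronger readings are tempting, and the documents do not support them.

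- **That about 10% undosed is expected.** The documents give a 10% dropout without saying what share is undosed, and they allow repeat inductions, so 10% is an upper case. The pass rates are still not a floor, as step 2 shows.
- **That the SAP names no primary analysis at all.** It ranks the two imputations. Only the ranking of ITT, mITT and PP is missing.
- **That balanced dropout always makes the rule conservative.** False claims first rise, to about 6.2% at 1% undosed, and fall below the no-dropout level only from about 3%.
- **That PP is known to inflate false claims by a given amount.** PP drops anyone dosed once, including a period-1 failure who does not return. The size depends on an assumed non-return share. It also depends on how far the discretion over a later visit in Protocol 7.3 extends, which the text leaves unclear.

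**What to change.** In SAP 6.5:

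1. Name one deciding analysis: all periods in which study drug was injected, keeping subjects dosed in only one period. Score missing = failure only where drug was injected and the 30-minute outcome is missing.
2. Apply the 5% G-Pen cap and the risk difference to that set.
3. Replace unpaired `riskdiff` with a pre-specified paired score-type interval that does not collapse at 0 against 0. One option is the Newcombe hybrid-score interval: Wilson limits for each drug, with the within-subject correlation taken from subjects dosed twice. It gives 3.2% for 0/116 against 0/117.
4. Keep all-randomised missing = failure, missing = success and PP as sensitivity analyses.
5. Tabulate undosed periods by assigned drug, period and reason.

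The cost is SAP wording, one interval and one table, with no new data or subjects. The deciding analysis would not be strict ITT and would treat undosed periods as uninformative under an unblinded investigator; the table in item 5 is there to check that. The power cost is in step 4 of the working: the full change loses to the SAP rule below about 3% undosed and gains above it.

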5.1.3 Per-Protocol Population (PP)

The Per-Protocol (PP) population is defined as all randomized patients who during both study periods successfully receive a dose of both study drugs (G-Pen followed by GlucaGen Hypokit or GlucaGen Hypokit followed by G-Pen) and have no any major protocol deviations. The actual treatment received will be used for analysis.

Primary endpoint comparison and secondary efficacy analyses will be performed for ITT, mITT and PP populations.

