5.1.5 Treatment groups

For summary statistics, subjects will be presented in two different ways, as applicable to the type of analysis:

- by planned treatment sequence of randomized subjects (GlucaGen Hypokit – G-Pen and G-Pen – GlucaGen Hypokit). This presentation and analysis will be used optionally

for descriptive outputs, but generally will not be used for analysis of the primary objective.

- by planned/actual treatment of subject in each treatment period (GlucaGen Hypokit and G-Pen). This presentation and analysis will be used for all primary and secondary endpoints, and optionally for descriptive outputs (disposition, demographics, etc.).

Planned treatment will be used for ITT population analyses and actual treatment received (by Period) will be used for mITT, PP and Safety population analyses.

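### The same-drug-twice rule in SAP 6.5 conflicts with the SAP's own ITT and mITT definitions: it discards an observed visit and scores the drug not given as a failure

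*SAP*

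**What the plan says.** Three parts of the SAP bear on a subject who is given the same drug in both periods.

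- **Population definitions.** For ITT (SAP 5.1.1), the subject's "randomized treatment will be used for analysis regardless of the actual treatment received". For mITT (SAP 5.1.2), "The actual treatment received will be used for analysis". SAP 5.1.5 repeats both: "Planned treatment will be used for ITT population analyses and actual treatment received (by Period) will be used for mITT, PP and Safety population analyses".
- **The special rule in SAP 6.5.** For such a subject, "only the visit with the planned treatment received will be included in the primary analysis and the subject will be considered a failure" for the other drug. The scope is explicit: the subject counts as "a failure in the primary analysis for the for unreceived treatment administration (ITT, mITT"), so both populations are named. The next sentence limits all other analyses to the planned treatment received as well.
- **The general rule in SAP 6.5.** "Subjects who are missing the primary endpoint for a study treatment will be considered as having a failure in the primary analysis" for that treatment, in ITT and mITT. In a sensitivity analysis, "all missing data will be considered a success".

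PP membership (SAP 5.1.3) requires that subjects "successfully receive a dose of both study drugs", so a same-drug-twice subject is not in PP.

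Non-inferiority (SAP 6.5) needs an upper 95% limit of at most 5 percentage points for the difference in failure rates, G-Pen minus GlucaGen. It also needs a G-Pen failure rate of at most 5%.

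**The concern.** The wrong-drug visit has an observed glucose outcome. The ITT definition places it under the planned drug, and the mITT definition places it under the drug injected. SAP 6.5 uses it in neither population and does not present itself as an exception to either definition.

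A handling error is then scored as lack of efficacy, against a drug that was not injected at the visit in question. SAP 4.2 expects response rates close to 100%, so failure counts should be small and one imputed failure can matter against a 5-point margin. No listed analysis brings the discarded result back. PP excludes the subject. The missing-as-success run could at most reverse the imputed failure, and the SAP does not say whether a drug never given counts as missing. SAP 6.6.1 applies the same test to the secondary binary endpoints, with no sensitivity analyses.

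**Working it through.** **1. The texts side by side.** Take a subject planned G-Pen then GlucaGen who receives G-Pen twice.

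| Basis | Period 1 (planned and given G-Pen) | Period 2 (planned GlucaGen, given G-Pen) | Failure imputed? |
|---|---|---|---|
| ITT, SAP 5.1.1/5.1.5 | observed, G-Pen | observed, GlucaGen | no; nothing is missing |
| mITT, SAP 5.1.2/5.1.5 | observed, G-Pen | observed, G-Pen | GlucaGen, if the general missing-as-failure sentence is applied |
| SAP 6.5 special rule, both sets | observed, G-Pen | discarded | GlucaGen |

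In ITT both steps depart from the definition. In mITT the clear departure is the discarded visit.

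**2. Inputs.**
- Denominator: 122 randomized (SAP 4.2). This reproduces as 111 × 1.10 = 122.1. The 111 cannot be reproduced, because no odds-ratio margin or within-subject correlation is stated, but nothing here depends on it.
- Interval: the SAP Appendix 2 code tabulates treatment by response with a risk-difference option, so it is unpaired. Wald limits are assumed as its default.
- Failure counts: assumed for illustration. The affected subject is assumed to respond at both visits.

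**3. Formula.** With failure proportions p_G and p_C on n_G and n_C:

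upper limit = (p_G − p_C) + 1.96 × √[p_G(1 − p_G)/n_G + p_C(1 − p_C)/n_C].

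One imputed failure moves the point estimate by 1/122 = 0.82 points.

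**4. G-Pen given twice,** starting from 3 G-Pen and 0 GlucaGen failures.

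| Basis | G-Pen | GlucaGen | Difference | Upper limit | Within 5? |
|---|---|---|---|---|---|
| ITT definition | 3/122 | 0/122 | 2.46 | 2.46 + 1.96 × 1.402 = 5.21 | no |
| SAP 6.5 rule | 3/122 | 1/122 | 1.64 | 1.64 + 1.96 × 1.622 = 4.82 | yes |
| Drug received, no imputation | 3/123 | 0/121 | 2.44 | 5.17 | no |
| Drug received, missing as failure | 3/123 | 1/122 | 1.62 | 4.78 | yes |

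The last two rows show why deleting the special rule alone would not settle mITT: the general sentence still adds the GlucaGen failure.

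**5. GlucaGen given twice,** starting from 2 versus 0.
- ITT definition: 2/122 versus 0/122, 1.64 + 1.96 × 1.150 = 3.89, passes.
- SAP 6.5 rule: 3/122 versus 0/122, 5.21, fails.

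Each such subject also uses one of the six G-Pen failures that the 5% cap allows (6/122 = 4.9%; 7/122 = 5.7%).

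**6. Both directions from one starting point.** From 3 versus 0 (5.21), a G-Pen-twice subject gives 4.82, a change of −0.39 points. A GlucaGen-twice subject gives 4 versus 0, upper limit 6.44, a change of +1.23 points.

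**The case against.** **The specific rule governs.** SAP 6.5 names this case and its scope, so a programmer can read it as the specific provision overriding the general ones. That is a fair reading. What remains is that neither SAP 6.5 nor the definitions declare an exception, and the definitions prescribe a different result.

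**mITT is only partly contradicted.** This stands. The retained visit is analysed under the drug received, and the imputed failure follows from the general sentence too. A reader might infer that both steps breach the mITT definition; the text supports that only for ITT.

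**The rule does not lean toward G-Pen.** This also stands. A reader might infer from the G-Pen-twice case that the rule favours non-inferiority. It applies equally to GlucaGen given twice, and in the example above the adverse shift in the limit is about three times the favourable one.

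**The alternative has its own weakness.** Scoring by planned drug in ITT credits or charges a drug with a response to the other one, which can dilute a real difference. That is a true cost, but it is what SAP 5.1.1 already prescribes, and the mITT analysis by drug received complements it.

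**It may never happen.** Staff know the treatment (SAP 4.4), the assignment is shown in the data capture system (Protocol 8.3), and the two products are an auto-injector and a reconstitution kit. The documents give no expected frequency. This limits the importance of the point but does not remove the conflict.

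**Conclusion.** The conflict is in the text. For a same-drug-twice subject, SAP 6.5 contradicts the ITT definition in both steps, and the mITT definition in discarding the observed visit. Each imputed failure moves the difference by 0.82 points. That is 16% of the margin (0.82/5) on the point estimate, but it would be wrong to read it as the effect on the decision. The decision uses the upper limit, which moved by −0.39 to +1.32 points in the examples (3.89 to 5.21 being the largest). One such subject can change the conclusion in either direction.

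These sizes rest on assumed failure counts, an affected subject who responds at both visits, 122 per drug before any reassignment, and unpaired Wald limits. In ITT, if the wrong-drug visit were itself a failure, the definition and SAP 6.5 would give the same count. With no such subject the rule has no effect. This is a minor point that is cheap to correct.

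**What to change.** Delete the same-drug-twice rule from SAP 6.5 and state instead:

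- **ITT:** score each observed outcome under the drug planned for that period (SAP 5.1.1).
- **mITT:** score each observed outcome under the drug received in that period (SAP 5.1.2 and 5.1.5).
- **General missing-as-failure sentence:** in mITT, apply it only to a drug that was injected but has no endpoint, not to a drug never injected. Without this amendment the imputed failure stays in mITT.

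If the sponsor prefers to keep the rule, declare it an exception in SAP 5.1.1, 5.1.2 and 5.1.5, and add a sensitivity analysis that uses the discarded visit.

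The cost is a short SAP edit before database lock, with no change to conduct, data collection or sample size. The statistical cost is that ITT attributes a response to a drug that did not produce it for any such subject, and that mITT denominators may differ slightly between drugs.
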